6.5.3. Sensitivity and Subgroup Analysis

Sensitivity analysis for key efficacy endpoints will be performed with the same methods described above based on the mITT Set and mITT-1 Set, with cases counted starting from randomization in Part 2. A sensitivity analysis will be performed based on a modified version of the endpoint definition, including COVID-19 non-RT-PCR tests.

Subgroup analysis may be done for the following subgroups:

- Sex (male, female)
- SARS-CoV-2 status at baseline
- Maternal COVID-19 vaccine status
- Maternal COVID-19 infection status
- Breastfeeding history
- Race
- Ethnicity

6.6. Interim Analyses

Part 1: Interim analyses of safety and immunogenicity will be performed after all treated participants in one or both arms have completed 28 days after the last dose of mRNA-1273.214. Note that two interim analyses will be performed. The Arm 2 interim analysis may include data from Arm 1.

Part 2: An interim analysis of safety and immunogenicity will be performed after all participants have completed 28 days after the last dose of mRNA-1273.214. This interim analysis will be considered the primary analysis for immunogenicity.

The final analysis of all endpoints will be performed after all participants have completed all planned study procedures and after the database is cleaned and locked. Results of this analysis will be presented in an end of study clinical study report (CSR), including individual listings.

6.7. Data Safety Monitoring Board

Safety oversight will be under the direction of a DSMB composed of external, independent consultants with relevant expertise. Members of the DSMB will be independent from study conduct and free of conflict of interest. The DSMB will operate under the rules of an approved charter that will be written and reviewed at the organizational meeting of the DSMB. Details regarding the DSMB composition, responsibilities, procedures, and frequency of data review will be defined in its charter. Statistical analysis outputs for the DSMB review will also be specified in the charter.

7. Changes from Planned Analyses in Protocol

On 18Sep2023, the study initiated an enrollment pause in direct response to emergency use authorization of an updated COVID-19 vaccine in children 6 months of age and older in the United States. Prior to the enrollment pause, 18 participants were enrolled in Part 1 Arm 2. As a result, the Part 1 Arm 2 interim analysis will be conducted after 18 participants have completed 28 days after last dose of mRNA-1273.214 rather than after the total planned enrollment in this arm (50 participants). This change does not impact the primary and/or key secondary objectives/hypotheses or the related statistical methods.

8. References

Department of Health and Human Services (DHHS), Food and Drug Administration, Center for Biologics Evaluation and Research (US). Guidance for industry: Toxicity grading scale for healthy adult and adolescent volunteers enrolled in preventative vaccine clinical trials. September2007[cited2019 Apr 10][10 screens]. Available from: https://www.fda.gov/downloads/BiologicsBloodVaccines/GuidanceComplianceRegulatory Information/Guidances/Vaccines/ucm091977.pdf.

9. List of Appendices

9.1. Appendix A: Standards for Variable Display in TFLs

Continuous Variables: The precision for continuous variables will be based on the precision of the data itself. The mean and median will be presented to one decimal place more than the original results; the SD will be presented to two decimal places more than the original results; the minimum and maximum will be presented to the same precision as the original results.

Categorical Variables: Percentages will be presented to 1 decimal place. If the count is 0, the percentage will not be displayed. If the count equals the denominator, the percentage will be displayed as 100.

9.2. Appendix B: Analysis Visit Windows for Analysis

Safety and Immunogenicity Analysis will be summarized using the following analysis visit window for post injection assessments:

Step 1: If the safety and immunogenicity assessments are collected at scheduled visit, i.e. nominal scheduled visit, the data collected at scheduled visit will be used.

Step 2: If the safety and immunogenicity assessments are not collected at the scheduled visit, assessments collected at unscheduled visit will be used using the analysis visit windows described in Table 3 below.

If a subject has multiple assessments within the same analysis visit, the following rule will be used:

- If multiple assessments occur within a given analysis visit, the assessment closest to the target study day will be used.
- If there are 2 or more assessments equal distance to the target study day, the last assessment will be used.

Table 3 Visit Window

Visit	Target Study Day	Visit Window in Study Day									
Nasal Swabs for SARS	Nasal Swabs for SARS-CoV-2										
Day 1	1 (Date of First Injection)	1, Pre-first-dose									
Day 57 (Month 2)	57 (Date of Second Injection)	[2, 71]									
Day 85 (Month 3)	85	[72,161]									
Day 237 (Month 8)	237	[162, 330]									
Day 422 (Month 14)	422	≥331									
SARS-CoV-2 Serology	7										
Day 1	1 (Date of First Injection)	1, Pre-first-dose									
Day 85 (Month 3)	85	≥2									
Immunogenicity											
Day 1	1 (Date of First Injection)	1, Pre-first-dose									
Day 85 (Month 3)	85	[2,161]									
Day 237 (Month 8)	237	[162, 330]									
Day 422 (Month 14)	422	≥331									

9.3. Appendix C: Imputation Rules for Missing Prior/Concomitant Medications, Non-Study Vaccinations, and Maternal Prior/Concomitant Medications

Imputation rules for missing or partial medication start/stop dates are defined below:

- 1. Missing or partial medication start date:
 - If only Day is missing, use the first day of the month, unless:
 - The medication end date is after the date of first injection or is missing AND the start month and year of the medication coincide with the start month and year of the first injection. In this case, use the date of first injection
 - If Day and Month are both missing, use the first day of the year, unless:
 - The medication end date is after the date of first injection or is missing AND the start year of the medication coincide with the start year of the first injection. In this case, use the date of first injection
 - If Day, Month and Year are all missing, the date will not be imputed, but the medication will be treated as though it began prior to the first injection for purposes of determining if status as prior or concomitant.
- 2. Missing or partial medication stop date:
 - If only Day is missing, use the earliest date of (last day of the month, study completion, discontinuation from the study, or death).
 - If Day and Month are both missing, use the earliest date of (last day of the year, study completion, discontinuation from the study, or death).
 - If Day, Month and Year are all missing, the date will not be imputed, but the medication will be flagged as a continuing medication.

In summary, the prior, concomitant or post categorization of a medication is described in Table 4 below.

Table 4 Prior, Concomitant, and Post Categorization of Medications and Non-study Vaccinations

	Medication Stop Date									
Medication Start Date	< First Injection Date of IP	≥ First Injection Date and ≤ 28 Days After Last Injection	> 28 Days After Last Injection [2]							
< First injection date of IP [1]	P	P, C	P, C, A							
≥ First injection date and ≤ 28 days after last injection	-	С	С, А							
> 28 days after last injection [3]	-	-	A							

A: Post; C: Concomitant; P: Prior

^[1] includes medications with completely missing start date

^[2] includes medications with completely missing end date

^[3] on the day of last injection and the 27 subsequent days

9.4. Appendix D: Imputation Rules for Missing AE dates

Imputation rules for missing or partial AE start dates and stop dates are defined below:

- 1. Missing or partial AE start date:
 - If only Day is missing, use the first day of the month, unless:
 - The AE end date is after the date of first injection or is missing AND the start month and year of the AE coincide with the start month and year of the first injection. In this case, use the date and time of first injection, even if time is collected.
 - If Day and Month are both missing, use the first day of the year, unless:
 - The AE end date is after the date of first injection or is missing AND the start year of the AE coincides with the start year of the first injection. In this case, use the date of first injection
 - If Day, Month and Year are all missing, the date will not be imputed. However, if the AE end date is prior to the date of first injection, then the AE will be considered a pre-treatment AE. Otherwise, the AE will be considered treatment-emergent.
- 2. Missing or partial AE end dates will not be imputed.

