8.11.11. Time Period and Frequency for Collecting AE, AESI, MAAE, and SAE Information

Medical occurrences that begin before the start of IP dosing but after obtaining informed consent/assent will be recorded in the Medical History/Current Medical Conditions section of the eCRF and not in the AE section; however, if the condition worsens at any time during the study, it will be recorded and reported as an AE.

Adverse events may be collected as follows:

- Observing the participant
- Receiving an unsolicited complaint from the participant's parent(s)/LAR(s)
- Questioning the participant's parent(s)/LAR(s) in an unbiased and nonleading manner

Solicited ARs will be collected from the day of injection through 6 days after each dose. Other (unsolicited) AEs will be collected from the day of injection through 28 days after each dose.

Serious AEs, AESIs, and MAAEs will be collected from the start of IP dosing until the last day of study participation at the time points specified in the SoA (Table 1).

All SAEs and AESIs will be recorded and reported to the Sponsor or designee immediately and in all circumstances within 24 hours of becoming aware of the event via the EDC system. If a site receives a report of a new SAE or AESI from a study participant or receives updated data on a previously reported SAE or AESI and the eCRF has been taken offline, then the site can report this information on a paper SAE or AESI form using the SAE Mailbox, the SAE Hotline, or the SAE Fax line (Section 8.11.10).

An abnormal value or result from a clinical or laboratory evaluation can also indicate an AE if it is determined by the investigator to be clinically significant (eg, leads to dose modification or study drug discontinuation, or meets any serious criteria, or is considered an AESI). If this is the

Protocol: mRNA-1273-P206, Original

case, it must be recorded in the source document and as an AE on the appropriate AE form(s). The evaluation that produced the value or result should be repeated until that value or result returns to normal or is stabilized and the participant's safety is not at risk.

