3.1. Primary Endpoints

The primary safety objective for Part 1 and Part 2 will be evaluated by the following safety endpoints:

- Solicited local and systemic adverse reactions (ARs) through 7 days after each injection
- Unsolicited adverse events (AEs) through 28 days after each injection
- Medically attended AEs (MAAEs) throughout the entire study period
- Serious AEs (SAEs) throughout the entire study period
- AEs of special interest (AESIs) throughout the entire study period
- AEs leading to discontinuation from study participation postdose throughout the entire study period

The primary immunogenicity objective to infer effectiveness of the mRNA-1273.214 vaccine for Part 2 will be evaluated by:

- Co-primary Endpoint: geometric mean (GM) value of antibodies (Ab) against SARS-CoV-2 VOC (Omicron) at 28 days after the second dose of mRNA-1273.214 compared with that of the adult participants at Day 57 (28 days after the second dose) in Study mRNA-1273-P301 dosed with mRNA-1273 (100 μg, 2 doses 28 days apart) primary series
- Co-primary Endpoint: seroresponse rate (SRR) against SARS-CoV-2 VOC (Omicron) at 28 days after the second dose of mRNA-1273.214 compared with that of the adult participants at Day 57 (28 days after the second dose) in Study

mRNA-1273-P301 dosed with mRNA-1273 (100 μg , 2 doses 28 days apart) primary series

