- b) study day on or after the date of the first injection but before the second injection (if applicable) will be calculated as: date of assessment/event date of the first injection + 1;
- c) study day on or after the date of the second injection will be calculated as: date of assessment/event date of the second injection + 1; if study day is on the same day as the second injection, date and time will be compared with the second injection date and time. If time is prior to the time of second injection, then study day is calculated as: date of assessment/event date of the first injection + 1; If it is after the time of second injection or the time is missing or not available then study day is calculated as: date of assessment/event date of the second injection + 1.

For calculation regarding antibody levels/concentrations, antibody values reported as below LLOQ will be replaced by 0.5 × LLOQ. Values that are greater than the upper limit of quantification (ULOQ) will be converted to the ULOQ if actual values are not available, and actual values will be used if available. Missing results will not be imputed.

The following analysis periods or stages for safety analyses will be used in this study:

- Up to 28 days after any vaccination: this stage starts at the day of each vaccination and continue through the earliest date of (the day of each vaccination and 27 subsequent days, next vaccination [if applicable]). This analysis period will be used as the primary analysis period for safety analyses including unsolicited AE, except for solicited AR, unless specified otherwise.
- Overall period (throughout the study): this analysis period starts at the first injection on Day 1 and continues through the earliest date of (study completion, discontinuation from the study, or death).

Unscheduled visits: Unscheduled visit measurements will be included in analysis as follows:

- In scheduled visit windows per specified visit windowing rules.
- In the derivation of baseline/last on-treatment measurements.
- In the derivation of maximum/minimum on-treatment values and maximum/minimum change from baseline values for safety analyses.
- In individual subject data listings as appropriate.

Visit windowing rules: The analysis visit windows for protocol-defined visits are provided in Appendix B.

Incomplete/missing data:

- Imputation rules for missing prior/concomitant medications, non-study vaccinations and procedures are provided in Appendix C.

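### SAP Appendix D has no second-injection exception for a missing AE start day, so some AEs that begin after Dose 2 drop out of the primary 28-day safety tables (minor)

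*SAP*

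**What the plan says.** SAP Appendix D gives a default for AE start dates: "If only Day is missing, use the first day of the month, unless" an exception holds. The exception has two conditions. The first is "The AE end date is after the date of first injection or is missing". The second is that "the start month and year of the AE coincide with the start month and year of the first injection". The AE then takes the date and time of the first injection. The rule for a missing day and month has the same structure. The second injection is mentioned in neither. On end dates Appendix D says "Missing or partial AE end dates will not be imputed", so nothing later in the appendix moves the start date back.

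The placement matters because SAP 3.1 lists "Unsolicited adverse events (AEs) through 28 days after each injection" as a primary safety endpoint. SAP 6.1 defines a stage that runs from each injection day through the 27 days after it, pooled over injections, and says: "This analysis period will be used as the primary analysis period for safety analyses including unsolicited AE". SAP 6.3.1 tabulates unsolicited AEs by vaccination group and stage. Protocol 8.11.11 sets the matching collection period: "Other (unsolicited) AEs will be collected from the day of injection through 28 days after each dose".

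**The concern.** The SAP treats the same ambiguity differently after the two injections. If the start day is unknown and the month is that of Dose 1, the AE is placed on the injection date. If the month is that of Dose 2, it is placed on the first of the month, normally before the injection. No reason is given for the difference.

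An AE that truly began after Dose 2 can therefore receive a date between the two windows. Routine unsolicited AEs are not meant to be collected in most of that interval, and the primary safety stage does not count it. At stake is the completeness of the pooled 28-day AE tables.

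**Working it through.** The documents give no figure on this point, so there is none to reproduce. The check is date arithmetic.

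**Inputs**
- Dose 2 is on Day 57, window −14/+7 days, extendable to +14 (Protocol 4.1.1.2 and Table 1): Day 43 to Day 64, or Day 71.
- Each window is the injection day plus 27 days (SAP 6.1): Days 1–28 for Dose 1, Days D to D+27 for Dose 2 on study day D.
- The imputation rule is Appendix D's.
- Assumptions, not in the documents: onsets uniform over the 28 days from Dose 2, injection dates uniform over the calendar, AE end date missing.

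**1. The exception cannot apply after Dose 2.** The earliest Dose 2 is 43 − 1 = 42 days after Dose 1. Two dates in one calendar month differ by at most 30 days, so the two injections never share a month.

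**2. Where the AE lands.** Let Dose 2 fall on day d of its month. The first of that month is study day D − (d − 1). This is before Dose 2 if d ≥ 2, and after the Dose 1 window if D − (d − 1) > 28, that is d ≤ D − 28. The AE is outside both windows for d = 2–15 (D = 43), 2–22 (D = 50) and 2–29 (D = 57).

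Example: Dose 1 on 20 Jan 2023, Dose 2 on 17 Mar 2023. An AE beginning on 20 Mar but recorded only as March 2023 is set to 1 Mar, study day 57 − 16 = 41. The Dose 1 window closed on 16 Feb, and Dose 2 is 16 days later.

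**3. How often.** In a month of L days, min(28, L − d + 1) of the 28 onset days fall in Dose 2's own month. Onsets in the following month are imputed to the first of that month, which is still inside the Dose 2 window, so they are unaffected. The share outside both windows is the sum of min(28, L − d + 1) over the affected d, divided by 28 × L. For same-month onsets only, the divisor is the sum over all d: 462 for L = 30 and 490 for L = 31.

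| Dose 2 on | L = 30, all onsets | L = 31, all onsets | Enumeration, all onsets | Enumeration, same-month onsets |
|---|---|---|---|---|
| Day 43 | 314/840 = 37.4% | 326/868 = 37.6% | 37% | 67% |
| Day 50 | 398/840 = 47.4% | 417/868 = 48.0% | 48% | 86% |
| Day 57 | 433/840 = 51.5% | 459/868 = 52.9% | 52% | 94% |

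The enumeration ran over 1,461 consecutive Dose 1 dates and the true calendar. For Dose 2 on Day 64 or 71 it gives 52% and 94% again. By calendar day of Dose 2, with Dose 2 on Day 57, the share outside both windows is 0% for the 1st, 99.8% for the 2nd, 59% for the 15th and 12% for the 28th.

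**4. With an exception for the second injection.** An AE that truly starts on or after Dose 2 cannot end before it, so it meets the end-date condition and takes the Dose 2 date. None is lost at any interval tested. SAP 6.1 counts an event on the Dose 2 date with no time as after Dose 2, so the placement holds.

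**The case against.** **Few dates are affected.** Onset time is a required AE item (Protocol 8.11.9), visits and calls are frequent around Dose 2, and monitors verify source data. The documents give no count of partial dates. This stands: every percentage above is conditional on a missing start day, and the absolute number is probably small.

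**The consequences are limited.** The AEs remain treatment-emergent and appear in the overall-period summaries and listings. The safety summaries are descriptive, and no hypothesis depends on them. SAEs, MAAEs, AESIs and AEs leading to discontinuation are followed for the whole study, and solicited reactions come from the eDiary. A participant with another AE inside a window is still counted. All this stands too, and it keeps the point minor.

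**Any convention misplaces something.** True, but the SAP has already chosen its convention for Dose 1, and the protocol's collection period favors the same choice for Dose 2.

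Two stronger readings are tempting, and the documents do not support them:
- *AEs are attributed to the wrong dose.* Some are indeed dated into the Dose 1 window, chiefly when Dose 2 is early. But the 28-day stage pools both injections, and SAP 6.3.1 lists no unsolicited AE table by dose. SAP 5.9 does define a Safety Set for each injection, but SAP 6.3.1 bases its percentages on the overall Safety Set. An AE moved into the Dose 1 window stays in the planned table. The share leaving the Dose 2 window is therefore the wrong measure; only the share outside both windows counts.
- *The vaccine and placebo comparison is biased.* The same rule applies to both arms, and nothing in the documents suggests that partial dates differ between them.

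**Conclusion.** The gap is real and minor. As written, Appendix D dates a day-missing AE that starts after Dose 2 in Dose 2's month before Dose 2, unless Dose 2 was given on the 1st. Such AEs usually drop out of the primary 28-day tables: 67% to 94% of same-month onsets, or 37% to 52% of all day-missing onsets in the 28 days from Dose 2, for Dose 2 on Day 43 to Day 57. These figures rest on uniform onsets, uniform injection dates and a missing end date.

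The effect on reported percentages cannot be estimated without the number of partial dates. As an illustration only, one participant lost from the count shifts a percentage by 1/18 = 5.6 points in Part 1 Arm 2 as enrolled (SAP section 7), or by 1/300 = 0.3 points in a planned Part 2 arm. Even that requires the participant to have no other AE in either window.

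**What to change.** Add to Appendix D, before database lock:

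> If only the day is missing, the AE start month and year equal those of the second injection, and the AE end date is on or after the second injection date or is missing, use the date of the second injection.

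Review the rule for a missing day and month at the same time, since it has the same first-injection-only exception. Also say how a partial end date is read in this test, because end dates are not imputed.

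The cost is a short text change and minor programming. The statistical downside is that some AEs that began earlier in that month and were still ongoing at Dose 2 would be counted after it. With Dose 2 on Day 57, for onsets on Days 29–56, this affects 7% of 3-day AEs, 19% of 7-day AEs and 52% of those with a missing end date. The SAP already accepts this kind of error under its Dose 1 exception. If the sponsor prefers the present rule, the SAP should state why the two injections are treated differently.

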9.5. Appendix E: Schedule of Assessments (Parts 1 and 2)

Visit Number	0	1	2	3		4	5	6	7	-	-	8	-	-	9	USV
Type of Visit	C	C	C	TM	SFU	C	C	TM	С	SF	U	C	C SFU		С	C
Month Time Point		M0	M0		SC	M2	M2		М3	eDiary	SC	M8	eDiary	SC	M14	Up to M14
Study Visit Day	D-28 to D-1 (Screening) ¹	D1 (Baseline)	D4 ²	D8	D29 ³	D57 ⁴	$\mathrm{D}60^2$	D64 ⁴	D854.5	Every 4 weeks D99–D211 ^{3, 4}	Every 4 weeks D113-D225 ^{3, 4}	D237,3	Every 8 weeks D265-D377 ^{4, 6}	Every 8 weeks D293-D405 ^{3, 4}	D422 365 days after D57 ^{3, 4}	Unscheduled Visit ^{7,8}
Window Allowance (Days)	-	-	± 1	+ 3	+3	-14/+ 7	± 1	+ 3	-14/+ 7	± 7	± 7	± 14	± 7	± 7	± 14	N/A
Days Since Most Recent Injection	-	0	3	7	28	56	3	7	28	-	-	180	-	-	365	
ICF, demographics, concomitant medications, medical history ⁹	X															
Review of inclusion and exclusion criteria	X	X														
Physical examination and vital signs including length/height, weight and body temperature ¹⁰	X	X	X			X	Х		X			Х			X	X
Randomization		X														
Study injection ¹¹		X				X										
Blood sample for vaccine immunogenicity ¹²		X			_				X			X			X	

Visit Number	0	1	2	3		4	5	6	7		-	8	-	-	9	USV
Type of Visit	С	C	C	TM	SFU	C	C	TM	C	SF	U	C	SF	TU	С	C
Month Time Point		M0	M 0		SC	M2	M2		M3	eDiary	SC	M8	eDiary	SC	M14	Up to M14
Study Visit Day	D-28 to D-1 (Screening) ¹	D1 (Baseline)	$\mathrm{D4}^2$	D8	D29 ³	D57 ⁴	$D60^2$	D64 ⁴	D854.5	Every 4 weeks D99_D211 ^{3, 4}	Every 4 weeks D113-D225 ^{3, 4}	D237,3	Every 8 weeks D265-D377 ^{4, 6}	Every 8 weeks D293-D405 ^{3, 4}	D422 365 days after D57 ^{3, 4}	Unscheduled Visit ^{7,8}
Window Allowance (Days)	-	-	± 1	+ 3	+3	-14/+ 7	± 1	+ 3	-14/+ 7	± 7	± 7	± 14	± 7	± 7	± 14	N/A
Days Since Most Recent Injection	-	0	3	7	28	56	3	7	28	-	-	180	-	-	365	
Blood sample for SARS- CoV-2 surveillance ¹³		X							X							
Nasal swab sample for SARS-CoV-2 ¹³		X				X			X			X			X	X
Surveillance for COVID-19/illness visit ⁷				X	X	X		X	X	X	X	X	X	X	X	X
eDiary activation for recording solicited ARs (7 days) ⁸		X				X										
Review of eDiary data			X	X			X	X								
Follow-up safety telephone calls ¹⁴					X						X			X		
Recording of unsolicited AEs		X	X	X	X	X	X	X	X							

Visit Number	0	1	2	3		4	5	6	7	-	-	8	-	=	9	USV
Type of Visit	C	С	C	TM	SFU	C	C	TM	C	SF	'U	C	C SFU		C	C
Month Time Point		М0	M0		SC	M2	M2		М3	eDiary	SC	M8	eDiary	SC	M14	Up to M14
Study Visit Day	D-28 to D-1 (Screening) ¹	D1 (Baseline)	D4 ²	D8	D29 ³	D57 ⁴	$\mathrm{D}60^2$	D64 ⁴	D85 ^{4, 5}	Every 4 weeks D99_D211 ^{3, 4}	Every 4 weeks D113-D225 ^{3, 4}	D237,3	Every 8 weeks D265-D377 ^{4, 6}	Every 8 weeks D293-D405 ^{3, 4}	D422 365 days after D57 ^{3, 4}	Unscheduled Visit ^{7, 8}
Window Allowance (Days)	-	-	± 1	+ 3	+3	-14/+ 7	± 1	+ 3	-14/+ 7	± 7	± 7	± 14	± 7	± 7	± 14	N/A
Days Since Most Recent Injection	-	0	3	7	28	56	3	7	28	-	-	180	-	-	365	
Recording of MAAEs, SAEs, and AESIs and concomitant medications and procedures relevant to or for the treatment of the MAAE and SAE ¹⁵		X	X	х	X	X	X	X	Х	х	Х	х	X	X	х	X
Recording of concomitant medications and procedures and nonstudy vaccinations ¹⁶		X	X	X	X	X	X	X	X		X	X		X	X	X

Abbreviations: AE = adverse event; AESI = adverse event of special interest; AR = adverse reaction; C = clinic visit; COVID-19 = coronavirus disease 2019; D = day; eCRF = electronic case report form; EDC = electronic data capture; eDiary = electronic diary; FDA = Food and Drug Administration; ICF = informed consent form; IRB = institutional review board; LAR = legally acceptable representative; M = month; MAAE = medically attended adverse event; N/A = not applicable; RT-PCR = reverse transcriptase polymerase chain reaction; SAE = serious adverse event; SARS-CoV-2 = severe acute respiratory syndrome coronavirus 2; SC = safety (telephone) call; SFU = safety follow-up; TM = telemedicine visit or call; USV= unscheduled visit.Note: In accordance with FDA Guidance on Conduct of Clinical Trials of Medical Products During COVID-19 Public Health Emergency (FDA March 2020), investigators may convert study site visits to home visits or telemedicine visits (with the exception of Screening, Day 1, Day 57, Day 85, Day 237, and Day 422) with the approval of the Sponsor (home visits also require site IRB approval).

^{1.} Screening Visit and Day 1 may be combined on the same day. Additionally, the Screening Visit may be performed over multiple visits if performed within the 28-day screening window.

- 2. Day 4 and Day 60 clinic visits will only be performed in Part 1 of study.
- 3. Safety follow-up via a safety telephone call will be performed on Day 29, every 4 weeks from Day 113 to Day 225, and every 8 weeks from Day 293 to Day 405.
- 4. If the visit for the second dose (Day 57) is disrupted and cannot be completed at Day 57 (-14/+7 days) as a result of the COVID-19 pandemic (self-quarantine or disruption of study site activities following business continuity plans and/or local government mandates for "stay at home" or "shelter in place"), the visit window may be extended to Day 57
- + 14 days. When the extended visit window is used, the remaining study visits should be rescheduled to follow the intervisit interval from the actual date of the second dose.
- 5. All scheduled study visits should be completed within the respective visit windows. If the participant is not able to attend a study site visit as a result of the COVID-19 pandemic (self-quarantine or disruption of study site activities following business continuity plans and/or local government mandates for "stay at home" or "shelter in place"), a remote evaluation via a telemedicine visit or call should be conducted in place of the study site visit (except for dosing visits and visits that require a blood draw). The remote evaluation should encompass all scheduled visit assessments that can be completed remotely, such as assessment for AEs and concomitant medications (eg, as defined in scheduled safety telephone calls). Home visits will be permitted for all nondosing visits, with the exception of screening, if a participant cannot visit the study site as a result of the COVID-19 pandemic. Home visits must be permitted by the study site IRB and the participant's parent(s)/LAR(s) via informed consent and have prior approval from the Sponsor (or its designee).
- 6. Safety follow-up via an eDiary questionnaire will be performed every 4 weeks from Day 99 to Day 211 and every 8 weeks from Day 265 to Day 377.
- 7. An unscheduled visit may be prompted by reactogenicity issues, illness visit criteria for COVID-19, or new or ongoing AEs. If a participant meets the pre-specified criteria of suspicion for COVID-19, the participant will be asked to return within 72 hours or as soon as possible to the study site for an unscheduled illness visit to include a nasal swab sample (for RT-PCR testing to evaluate for the presence of SARS-CoV-2 infection) and other clinical evaluations. If a study site visit is not possible, a home visit may be arranged to collect the nasal swab sample and conduct clinical evaluations. The study site may collect an additional nasal swab sample for SARS-CoV-2 testing to be able to render appropriate medical care for the study participant as determined by local standards of care. Additionally, clinical information will be carefully collected to evaluate the severity of the clinical case.
- 8. At each injection visit, participants' parent(s)/LAR(s) will record data into the eDiary starting approximately 30 minutes after injection under the supervision of the study site staff to ensure successful entry of assessment. Participants' parent(s)/LAR(s) will continue to record entries in the eDiary after they leave the study site, preferably in the evening and at the same time each day, on the day of injection and for 6 days following injection. Capturing details of ARs in the eDiary should not exceed 7 days after each vaccination. If a solicited local or systemic AR continues beyond Day 7 after vaccination, the event should be reviewed by the study site staff either via a telephone call or at an unscheduled study site visit.
- 9. Verbal medical history is acceptable.
- 10. A full physical examination and vital signs assessments, including length/height, weight, and body temperature, will be performed at the Screening Visit (and on Day 1, if Day 1 and Screening Visit occur on separate days). Symptom-directed physical examinations and vital signs assessments will be performed on Day 1, Day 4 (in Part 1), Day 57, Day 60 (in Part 1), Day 85, Day 237, Day 422, and USV, and may be performed at other time points at the discretion of the investigator. Body temperature should be measured on each injection day prior to injection. Body temperature must be measured via the axillary route and any axillary reading of $\geq 37.8^{\circ}$ C/ $\geq 100^{\circ}$ F may be confirmed by a rectal measurement. On each injection day before injection and again 7 days after injection, the injection site should be examined. Any clinically significant finding identified during a study visit should be reported as an MAAE. Participants who are febrile ($\geq 38.0^{\circ}$ C/ $\geq 100.4^{\circ}$ F) before injection on Day 1 or Day 57 must have the visit rescheduled within the relevant visit window to receive the injection. Afebrile participants with minor illnesses may be injected at the discretion of the investigator.
- 11. Study injection postdose observation will be 60 minutes for Part 1 and 30 minutes for Part 2.
- 12. On Day 1, sample must be collected prior to randomization and dosing. If a Day 1 (baseline) blood sample cannot be obtained, the participant could be rescheduled within the allowable screening period one time. If a blood sample still cannot be obtained at the rescheduled visit, then the participant will be considered a screen failure due to inability to satisfy inclusion criterion 3.
- 13. The nasal swab and blood sample (collected before dosing on each injection day and on other scheduled days per the SoA) will be used to ascertain the presence or history of SARS-CoV-2 infection via RT-PCR and serum binding antibody specific to SARS-CoV-2 nucleocapsid, respectively.
- 14. Medically qualified and trained study site personnel will call all participants to collect information relating to any MAAEs, SAEs, AEs leading to study withdrawal and information on concomitant medications associated with those events and any nonstudy vaccinations. In addition, study personnel will collect information on known participant exposure to someone with known COVID-19 or SARS-CoV-2 infection and on any COVID-19 symptoms the participant may experience.

- 15. A list of AESIs pertinent to this study is maintained by the Sponsor and provided to each investigator. All SAEs and AESIs will be reported to the Sponsor or designee immediately and in all circumstances within 24 hours of becoming aware of the event via the EDC system. If a site receives a report of a new SAE or AESI from a study participant or receives updated data on a previously reported SAE or AESI and the eCRF has been taken offline, then the site can report this information on a paper SAE or AESI form using the SAE Mailbox, the SAE Hotline, or the SAE Fax line.
- 16. All concomitant medications and procedures will be recorded through 28 days after each injection (through the completion of the Day 85 visit). All nonstudy vaccines given at any time during the study period should be recorded. All concomitant medications relevant to or for the treatment of an SAE, MAAE, or AESI will be recorded from Day 1 through the final visit (Day 422).
